7.3 DOSING RATIONALE: RISKS AND BENEFITS

7.3.1 Medication and Blinding US WorldMeds, LLC (Louisville, KY) will provide lofexidine (LFX). Alkermes, Inc. (Waltham, MA) will provide XR- NTX. Each site will have 20 XR-NTX kits before the study begins to endure immediate availability. The Penn Research Pharmacy will prepare blister packs with each day's planed doses in separate a compartment. Each compartment will be labeled with the dosing time on each inpatient study day.

Lofexidine will be provided as pink, 0.18 mg tablets; pregabalin as blue capsules for the 100 mg or placebo doses and as green capsules for the 25 mg or placebo doses. Medical staff will be able to reduce or withhold doses by not removing them from their compartment in the blister pack at their scheduled time of administration, after receiving a physician's order. Such an order is likely to be given after a clinically significant AE that appear to have been study medication-related.

Examples of possible AE's are: clinically-significant prolongation of the QTc or QRS; clinically significant (>20 mm) drop in blood pressure (BP) compared to the last reading; and/or drop in systolic BP of 20 mm or more standing, or 10 mm or more sitting to make it; excessive sedation or dizziness (can use manual blood pressure check if considered necessary). Subjects must exhibit mild to moderate opioid withdrawal prior to receiving the first dose of study medication (COWS >/=6,

SOWS >/= 4), and pass a naloxone challenge to show they are free of physiologic opioid dependence before receiving XT-NTX.

7.3.2 DOSING SCHEDULES

Table 2: LFX Dosing: all tablets are 0.18 mg

	Time	Day 1	Day 2	Day 3	Day 4	Day 5	Day 6	Day 7
All	0800	0.00	0.54	0.54	0.54	0.54	0.36	0.18
Groups								
	1200	0.54	0.54	0.54	0.54	0.36	0.18	0.18
	1600	0.54	0.54	0.54	0.54	0.36	0.18	0.18
	2000	0.54	0.54	0.54	0.54	0.36	0.18	0.18
	Total	1.62	2.16	2.16	2.16	1.62	0.90	0.72

Table 3: PGB and PGB-PLA Dosing (in mg)

	Time	Day 1	Day 2	Day 3	Day 4	Day 5	Day 6	Day 7
Group 1	0800	0	200	200	200	100	50	25
(PGB)	1200	100	100	100	100	75	25	25
	1600	100	100	100	100	75	25	25
	2000	200	200	200	200	150	100	25
	Total	400	600	600	600	400	200	100
Group 2	0800	0	PLAC	PLAC	PLAC	PLAC	PLAC	PLAC
(PGB-PLA)	1200	PLAC						
	1600	PLAC						
	2000	PLAC						
	Total	0	0	0	0	0	0	0

7.3.3 Dosing Guidelines:

As stated below investigators may choose to stop or reduce the dose of either Study Medication although BP and pulse changes are more likely to be due to lofexidine and sedation due to pregabalin.

- Patients can be started and continued on Study Medication if the pulse is 50 or above. Medication should be held if the pulse is <50.
- Patients can be started on Study Medications on Day 1 if COWS >/=6 and SOWS_>/= 4
- A study physician is required to hold the dose of Study Medication if the systolic BP is < 90 and/or the diastolic is <60. Investigators should hold both lofexidine and pregabalin until the next dosing time when they can be restarted if the vitals return to 90/60 or above.
- Hypotension is a potential side effect of lofexidine; sedation, dizziness, or light-headedness are
 potential side effect of pregabalin. A drop of 20 mm or more systolic and/or 10 mm or more diastolic;
 or significant lightheadedness or dizziness, are grounds for holding or reducing a dose of the
 medication that is the most likely cause. Investigators should use their judgement on which Study
 Medication to hold or reduce and by how much.
- **7.3.3.1** The following procedures will minimize risks associated with transient vs. persistent BP changes:
 - If the BP reading shows a pre-medication sitting and/or standing drop (orthostatic change) of more than 20mm systolic, and/or more than 10 mm diastolic, wait 2-3 minutes and repeat the sitting and standing BP.

- If the repeat readings are within the acceptable range as defined by the protocol, dosing can be continued as planned.
- If the repeated readings are not within this range as defined by the protocol, hydrate the patient and study medication should be administered at the next scheduled dosing time provided they are in an acceptable range, as defined by the protocol. Retest the BP within an hour. Depending on the results of the BP retest, the physician has the discretion to give full dose, reduced dose, or hold the dose of study medication until the next scheduled dosing time.

Dosing should be given per the protocol scheduled times of 8:00, 12:00, 16:00, and 20:00. However, when dosing cannot be given at the protocol scheduled times, Study Medication can be given up to 1 hour pre or post the scheduled dose time. On day 1, if dosing cannot be given at the 12:00 scheduled time, after 2 hours, wait until the next scheduled 16:00 dose. In case of scheduled dosing changes, medication cannot be scheduled less than a minimum of 3 hours apart.

- **7.3.4** Potential Risks: These include AEs to PGB, LFX, and XR-NTX (for those who transition to it); potential adverse interactions between PGB and LFX; and a small risk from venipuncture. Clinical trials are conducted under widely varying conditions thus adverse reaction rates in clinical trials cannot be directly compared to rates in clinical trials of another similarly-acting drug, and may not reflect the rates observed in clinical practice.
- **7.3.5_PGB associated AE's:** In controlled and uncontrolled trials across various patient populations during premarketing development more than 10,000 patients received PGB; approximately 5000 for 6 months or more; over 3100 for 1 year or more; and over 1400 for at least 2 years.
- **7. 3. 6** Most common AE's leading to discontinuation of PGB. In premarketing trials of all populations combined, 14% of patients treated with PGB and 7% of patients treated with placebo discontinued treatment prematurely due to AEs. AEs most frequently leading to discontinuation were dizziness (4%) and somnolence (3%). In the placebo group, 1% of patients withdrew due to dizziness and <1% withdrew due to somnolence. Other adverse reactions that led to discontinuation more frequently in the PGB group compared to placebo were ataxia, confusion, asthenia, thinking abnormal, blurred vision, incoordination, and peripheral edema (1% each).
- **7.3.7** Most common AE's in all pre-marketing controlled PGB studies. In premarketing controlled trials of all populations, dizziness, somnolence, dry mouth, edema, blurred vision, weight gain, and "thinking abnormal" (mostly difficulty with concentration/attention) were more commonly reported by subjects treated with PGB than placebo (≥5%, twice the placebo rate).
- **7.3.8_AE's Leading to Discontinuation in controlled PGB trials.** For those of neuropathic pain in patients with diabetic neuropathy: 9% of patients treated with PGB and 4% of patients treated with placebo discontinued prematurely due to AEs. In the PGB group, the most common reasons for discontinuation were dizziness (3%) and somnolence (2%). In comparison, <1% of placebo patients withdrew due to dizziness and somnolence. Other reasons for discontinuation with greater frequency in the PGB than placebo groups were asthenia, confusion, and peripheral edema. Each led to withdrawal in approximately 1% of patients. Table 4 lists AEs, regardless of causality, occurring in ≥1% of patients with neuropathic pain associated with diabetic neuropathy in the PGB group for which the incidence was greater than placebo. A majority of PGB patients had AEs with a maximum intensity of "mild" or "moderate".

Table 4: AE'S in trials of Neuropathic Pain Associated with

Diabetic Neuropathy in at least 1% of pregabalin-treated patients

Body system - Preferred term	75 mg/day [N=77]	150 mg/day [N=212] %	300 mg/day [N=321] %	600 mg/day [N=369] %	All PGB* [N=979] %	Placebo [N=459]
Body as a Whole						
Asthenia	4	2	4	7	5	2
Accidental injury	5	2	2	6	4	3
Back pain	0	2	1	2	2	0
Chest pain	4	1	1	2	2	1
Face edema	0	1	1	2	1	0
Digestive System						
Dry mouth	3	2	5	7	5	1
Constipation	0	2	4	6	4	2
Flatulence	3	0	2	3	2	1
Metabolic and Nutr	ritional					
Peripheral edema	4	6	9	12	9	2
Weight gain	0	4	4	6	4	0
Edema	0	2	4	2	2	0
Hypoglycemia	1	3	2	1	2	1
Nervous System						
Dizziness	8	9	23	29	21	5
Somnolence	4	6	13	16	12	3
Neuropathy	9	2	2	5	4	3
Ataxia	6	1	2	4	3	1
Vertigo	1	2	2	4	3	1
Confusion	0	1	2	3	2	1
Euphoria	0	0	3	2	2	0
Incoordination	1	0	2	2	2	0
Thinking abnormal [†]	1	0	1	3	2	0
Tremor	1	1	1	2	1	0
Abnormal gait	1	0	1	3	1	0
Amnesia	3	1	0	2	1	0
Nervousness	0	1	1	1	1	0
Respiratory System						
Dyspnea	3	0	2	2	2	1
Special Senses						
Blurry vision [‡]	3	1	3	6	4	2
Abnormal vision	1	0	1	1	1	0

^{*} PGB: pregabalin

[†] Thinking abnormal primarily consists of events related to difficulty with concentration/attention but also includes events related to cognition and language problems and slowed thinking.

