Note: Study medication will be provided in blister packs that are prepared by the PENN Investigational Drug Service and shipped to all three study sites. For the University of Pennsylvania, each blister pack will have a patient randomization number and the dosing schedule for each time on each inpatient study day, as summarized in the Study Schematics 4.0 below. For the two external sites, patient randomization will be generated by the site pharmacy or designated unblinded person, who receives the blister packs from the PENN Investigational Drug Service with the dosing schedule for each day.

The doses for each time of each day will be in separate compartments. Lofexidine will be 0.18 mg pink tables; pregabalin or pregabalin placebo will be in capsules. Blue capsules will contain 100 mg pregabalin or placebo; green capsules will contain 25 mg pregabalin or pregabalin placebo. These medications have not been used together and it is likely that doses will need to be held or reduced due to side effects. The most likely side effect from lofexidine is hypotension and/or bradycardia. The most likely side effect from pregabalin is sedation. Thus, in the event of hypotension, the next scheduled dose of lofexidine can be reduced or withheld. A similar adjustment can be made for excessive sedation (POSS score of 3 or 4; difficult to arouse, slurred speech, etc.) For the PENN site, medication counts will be done by the Investigational Drug Service (IDS) pharmacy for each subject. For sites outside PENN, medication counts will be done by the site or site pharmacy.

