- **7.4.4 ECG and Vital Signs.** ECGs will be reviewed each day before administration of the first dose of study medication. Medication will be withheld if there is clinically significant QTc prolongation. Vital signs will be checked sitting and standing pre-dose and 1-2 hours post dose. Study medication will be withheld if the seated systolic BP is below 90 systolic or below 60 diastolic, and/or if the pulse is <50. A study physician will be contacted for dosing instructions if the seated systolic BP is >20 mm, or >10 mm diastolic below the last reading. Study medications may also be withheld or reduced if there is excessive sedation or other clinically significant AE's that may be caused by study medication. First degree AV block is common and does not indicate a serious problem. Study medication should be stopped and the study cardiologist contacted if there is 2nd degree heart block.

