Subjects are admitted to the inpatient unit, randomized to one of the two study medication conditions, and will need to demonstrate withdrawal before starting study medications by having a COWS >/= 6 and a SOWS >/= 4. LFX and PGB dosing will begin at 12:00 on day 1 and a study drug taper will be done from days 5-7. Dose times follow the schedule outlined above and adjustments will be made based on BP changes and/or other AEs. Administration of LFX will be withheld or reduced in cases of dizziness or lightheadedness, clinically significant hypotension and/or the BP changes described above. We will explain to participants the importance for adequate oral hydration during the consenting process and throughout the detox. Similar procedures will be applied to PGB in cases of excessive sedation, dizziness, peripheral edema, or other problematic side effects that appear related that medication.

Dosing schedules are in Tables 2 and 3. Assessments for Day 1 through 7 include:

- 1) ECG is obtained before the 12:00 dose of study medications on Day 1 and before the 08:00 dose of study medications on Day 2-7
- 2) VAS is given before the first dose of study medication at 12:00 on Day 1 and before the 16:00 dose on Day 1. On Day 2-7, the VAS is given before the first dose of study medications at 08:00 and before the 16:00 dose of study medications
- 3) ISI given before the 12:00 dose of study medications on Day 1, and before the 08:00 dose of study medications on Days 2-7
- 4) COWS is given around 12:00 on Day 1 before the first dose of study medication; and around16:00 before the next dose of study medication. If subject is admitted without the requisite withdrawal (COWS >/= 6 and SOWS >/= 4), subsequent COWS and SOWS can be administered before the first dose of study medication until dosing criteria is met.
- 5) SOWS-G is given around 12:00 on Day 1 before the first dose of study medication; and around 16:00 before the next dose of study medication
- 6) POSS is given prior to all doses (08:00, 12:00, 16:00 and 20:00) of study medication
- 7) Sitting and standing blood pressure and pulse are taken prior to each dose of study medication and 1 to 2 hours after dosing, (can use manual blood pressure check if considered necessary)
- 8) Weight taken 1x at screen and Day 15 and recorded on the physical form
- 9) Adverse events/SAEs recorded daily
- 10) Concomitant medication records reviewed and recorded each day
- 11) C-SSRS is given at the end of each study day

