19.2 MEDICATION DISCONTINUATION CRITERIA

All randomized subjects are included in the intent-to-treat analysis. All subjects who prematurely discontinue treatment will be scheduled for a final evaluation and end-of trial visit (unless these two fall within 2 weeks of each other), and the follow up visit. Subjects are not dropped from all study activity unless they request to not be contacted or cannot be located for assessment.

Subjects will be informed at the consent session that medications may be held or discontinued due to intolerable side effects, hypotension or other problematic cardiovascular effects, or extreme lab values confirmed by a repeat test. (AST or ALT levels greater than 4 times upper limit of normal; elevated BUN, creatine kinase, or other evidence of renal damage). Subjects will also be informed at the consent session that he or she may be discontinued from study treatment due to: 1) Development or exacerbation of significant psychiatric or medical symptoms which necessitate admission to a medical unit or an intervention different from that provided by the protocol; 2) Clinical deterioration for any reason or a clinical status which necessitates inpatient admission; 3) Prolonged QTc after repeat ECG; 4) Blood pressure is less than 90 mm Hg (systolic) or less than 60 mm Hg (diastolic). For sitting to standing blood pressure (orthostatic change), if there is a change in systolic blood pressure of more than 20mm or diastolic blood pressure more than 10mm HG, the dosing nurse or physician may hold the lofexidine or pregabalin dose until the next dose and then recheck (can use manual blood pressure check if considered necessary). If at any point blood pressure is less than 90/60 the nurse or physician should also hold the lofexidine or pregabalin dose and consult a study physician. If for any dose, the blood pressure results remain below the previously stated minimum mmHg by the next scheduled dose, the next dose may be reduced or withheld. Dosing discontinuations can be discussed with the Lead PI and the medical monitor if it impacts subject continuation in the dosing part of the study. The reason the subjects misses their next dose of Study Medication or discontinues from Study Medication must be documented in the subject's casebook

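### Below 90/60 mm Hg, section 7.3.3 holds both drugs until blood pressure recovers, but section 19.2 says to hold one or the other and can be read as allowing a reduced dose while pressure is still low

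*Combined protocol and SAP*

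**What the plan says.** **Section 7.3.3 (Dosing Guidelines)** makes the hold mandatory: "A study physician is required to hold the dose of Study Medication if the systolic BP is < 90 and/or the diastolic is <60". It then says which drugs are held and when they may resume: "hold both lofexidine and pregabalin until the next dosing time when they can be restarted if the vitals return to 90/60 or above".

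**Section 7.4.4 (ECG and Vital Signs)** agrees on withholding: "Study medication will be withheld if the seated systolic BP is below 90 systolic or below 60 diastolic".

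**Section 19.2 (Medication Discontinuation Criteria)** uses the same 90/60 limit. Below it, "the nurse or physician should also hold the lofexidine or pregabalin dose and consult a study physician". If readings "remain below the previously stated minimum mmHg by the next scheduled dose, the next dose may be reduced or withheld".

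Two looser statements give no threshold and name only lofexidine. The note in **section 3.0** says that "in the event of hypotension, the next scheduled dose of lofexidine can be reduced or withheld". **Section 9.1.2** says "Administration of LFX will be withheld or reduced in cases of dizziness or lightheadedness, clinically significant hypotension and/or the BP changes described above".

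The section 3.0 note also gives the context: "These medications have not been used together and it is likely that doses will need to be held or reduced".

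**The concern.** A clinician with a reading below 90/60 needs two answers: which drug to stop, and whether anything may be given before pressure recovers. Sections 7.3.3 and 19.2 can be read to answer both differently.

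The situation is foreseeable. Section 7.4.3 lists hypotension, orthostatic hypotension and bradycardia among the lofexidine adverse events seen in at least 10% of patients. Section 7.4 gives a half-life of about 12 hours, with accumulation for up to 4 days on repeat dosing. Scheduled daytime doses are 4 hours apart, so pressure may well still be low at the next dosing time, which is where the two sections diverge. Exclusion criterion 7 in section 10.2 also lets patients with pressure below 90/60 enter case by case.

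What is at stake is the safety of patients on an untested combination, and whether three sites deliver the randomised drug in the same way to patients with the same readings.

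**Working it through.** The plan gives no figure to reproduce. The check is a comparison of the texts, followed by arithmetic on the dosing tables.

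**1. The rules side by side, at systolic <90 or diastolic <60**

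| Question | Section 7.3.3 | Section 7.4.4 | Section 19.2 |
|---|---|---|---|
| Is a hold directed at the first low reading? | Yes, required | Yes | Yes, with a study physician consulted |
| Which drug? | Both | Study medication, not split | Lofexidine or pregabalin |
| Pressure still low at the next dose? | Restart is tied to a return to 90/60 or above | Withheld; no reduced dose offered | Next dose may be reduced or withheld |

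**2. Which minimum does 19.2 mean?** The only minimum stated in that section is 90/60. Its other blood pressure trigger, an orthostatic fall of more than 20 mm systolic or 10 mm diastolic, is a change and not a floor. The natural reading is therefore that a reduced dose is permitted while pressure is below 90/60. The sentence just before it in 19.2, which calls for a hold and a physician consult whenever pressure is below 90/60, points towards the stricter reading. The section supports both.

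**3. Does other text settle it?**
- The section 3.0 note and section 9.1.2 name only lofexidine for hypotension and allow reduction or withholding.
- Section 7.1.6 lists pressure below 90 or 60 among the grounds for dose adjustment, without requiring a hold.
- The judgement-based rules in 7.3.3 and 7.3.3.1 concern a fall of 20/10 mm, which is a different trigger.
- No section is given precedence.

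**4. How often the rule applies.** From Tables 2 and 3 there are 3 dosing times on Day 1 and 4 on each of Days 2-7: 3 + 6 × 4 = 27 per patient. Section 9.1.2 has blood pressure taken before each one.

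**5. What one held dosing time removes on Days 2-4**
- Lofexidine: 0.54 / 2.16 mg = 25% of the day's dose.
- Pregabalin (or matching placebo) at 12:00 or 16:00: 100 / 600 mg = 16.7%.
- Pregabalin (or matching placebo) at 08:00 or 20:00: 200 / 600 mg = 33.3%.

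Under 7.3.3 both components are lost. If 19.2 is read as a hold of lofexidine alone, no pregabalin is lost. If it is read as a hold of pregabalin alone, no lofexidine is lost.

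**The case against.** The strongest reply is that this is loose drafting with little practical effect.

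- **Section 7.3.3 is the working instruction.** A dosing clinician would normally turn to it, and its hold is mandatory. The blood pressure text in 19.2 follows a list of what subjects are told at consent. This has some force, but those sentences in 19.2 address the nurse and physician directly, and nothing ranks the two sections.
- **The *or* may be inclusive.** Both drugs are due at every dosing time, so the phrase could mean whichever doses are due. That is possible, but 19.2 does not say so, and sections 3.0 and 9.1.2 pull towards lofexidine alone. It is also fair that an exclusive *or* does not itself favour lofexidine.
- **The reduced-dose reading is permissive only.** A patient still below 90/60 again meets the instruction to hold and consult. This stands, and it is why the point is ambiguity and not an instruction to dose.
- **A physician is always involved.** Section 7.3.1 requires a physician's order to reduce or withhold, and 19.2 requires a consult. This limits the risk, but the physician consulted still has two rules.
- **No frequency is shown.** This is correct. The percentages describe what a held dose removes, not how often the sections would lead to different actions.
- **Sections 3.0 and 9.1.2 are weak support.** They are summaries without a threshold and do not contradict a mandatory hold. They add to the ambiguity but do not create it.

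**Conclusion.** The concern holds. At one threshold the protocol gives two different wordings on which drug to hold, and can be read to differ on whether a reduced dose may be given before pressure recovers. Nothing says which prevails. It should be corrected; confidence that the conflict exists is high.

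Its practical size is unknown, because the documents give no rate of pressure below 90/60 at dosing. What can be stated is the exposure: 27 dosing times per patient, and a difference on Days 2-4 of 17% or 33% of the day's pregabalin or placebo between holding both drugs and holding lofexidine alone. That comparison assumes 19.2 is read as allowing a lofexidine-only hold.

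**What to change.** Amend section 19.2 to match 7.3.3 and 7.4.4:
- Below 90/60, hold both drugs.
- If pressure is still below 90/60 at the next scheduled dose, keep holding both and consult the study physician.
- Give no reduced dose until pressure is 90/60 or above.

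Have the section 3.0 note and section 9.1.2 refer to 7.3.3 instead of restating the rule, and bring the dose-adjustment wording in 7.1.6 into line. In the same edit, say whether the limit applies to seated readings only: 7.4.4 specifies seated pressure, while 7.3.3 gives no position.

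If the sponsor's clinicians prefer to hold lofexidine alone, that is a clinical choice, but that single rule should then appear in every one of these sections. The separate 20/10 mm orthostatic rule can stay judgement-based.

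The cost is protocol wording and a staff memo. The possible downside is slightly more held pregabalin or placebo doses at any site that had been holding lofexidine alone.
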